#### **8.4.1 Primary efficacy analysis**

Old text:

Both comparisons will be performed at the time of final analysis, after the latest of (1) approximately 135 SSE-FS events in subjects included in Comparison 1 as defined below; (2) approximately 75 SSE-FS events following ~~Week 24~~ in subjects included in Comparison 2 as defined below; and (3) the last subject has been followed for 30 days from last treatment. In the event the applicable number of events is not reached, the primary endpoint analysis will mature 7 years after the last subject has received last treatment.

Comparison 2: No further radium-223 dichloride treatment versus extended dosing: SSE-FS analysis from ~~24 weeks~~ in subjects receiving standard-dose regimen

H02: In a population of subjects treated with a regimen of up to 6 doses of 50 kBq/kg (55 kBq/kg after implementation of NIST standard update) (standard dose) radium-223 dichloride who survived SSE-free and are eligible for further radium-223 dichloride treatment at 24 weeks, population SSE-FS beyond ~~24 weeks~~ in subjects treated with a regimen of up to an additional 6 doses of 50 kBq/kg (55 kBq/kg after implementation of NIST update) (extended dose) radium-223 dichloride is equal to population SSE-FS beyond ~~24 weeks~~ in subjects receiving no further radium-223 dichloride treatment beyond the standard dose regimen, versus

HA2: In a population of subjects treated with a regimen of up to 6 doses of 50 kBq/kg (55 kBq/kg after implementation of NIST update) (standard dose) radium-223 dichloride who survived SSE-free and are eligible for further radium-223 dichloride treatment at 24 weeks, population SSE-FS beyond ~~24 weeks~~ in subjects treated with a regimen of up to an additional 6 doses of 50 kBq/kg (55 kBq/kg after implementation of NIST update) (extended dose) radium-223 dichloride is greater than population SSE-FS beyond ~~24 weeks~~ in subjects receiving no further radium-223 dichloride treatment beyond the standard dose regimen.

Comparison 2 will be an analysis of SSE-FS from 24 weeks ~~from randomization~~ in subjects surviving SSE-free to ~~24 weeks~~ completing and / or not discontinued from treatment. It will compare subjects in Treatment Arm A with subjects in Treatment Arm C.

New text:

Comparison 2: No further radium-223 dichloride treatment versus extended dosing: SSE-FS analysis from the 6th dose in subjects receiving standard-dose regimen

H02: In a population of subjects treated with a regimen of up to 6 doses of 50 kBq/kg (55 kBq/kg after implementation of NIST standard update) (standard dose) radium-223 dichloride who survived SSE-free and are eligible for further radium-223 dichloride treatment at 24 weeks, population SSE-FS beyond the 6th dose in subjects treated with a regimen of up to an additional 6 doses of 50 kBq/kg (55 kBq/kg after implementation of NIST update) (extended dose) radium-223 dichloride is equal to population SSE-FS beyond the 6th dose in subjects receiving no further radium-223 dichloride treatment beyond the standard dose regimen, versus

HA2: In a population of subjects treated with a regimen of up to 6 doses of 50 kBq/kg (55 kBq/kg after implementation of NIST update) (standard dose) radium-223 dichloride who survived SSE-free and are eligible for further radium-223 dichloride treatment at 24 weeks, population SSE-FS beyond the 6th dose in subjects treated with a regimen of up to an additional 6 doses of 50 kBq/kg (55 kBq/kg after implementation of NIST update) (extended dose) radium-223 dichloride is greater than population SSE-FS beyond the 6th dose in subjects receiving no further radium-223 dichloride treatment beyond the standard dose regimen.

Comparison 2 will be an analysis of SSE-FS from the 6th dose, in subjects surviving completion of to the 6th dose. It will compare subjects in Treatment Arm A with subjects in Treatment Arm C.

#### **8.4.2.2 Analyses of standard dosing and extended dosing from the 6th dose date**

Old text:

For the following secondary endpoint analyses, subjects will be classified into 2 treatment groups: (1) the “standard dose” treatment group, consisting of applicable ITT subjects in Treatment Arm A, and (2) the “extended dosing” treatment group, consisting of applicable ITT subjects in Treatment Arm C. For these analyses, the start date will be 24 weeks, and the 24 week ~~assessment~~ baseline will be used.

For secondary endpoint time-to-event analyses for these treatment groups, subjects included will have survived to the 24 week start date without having experienced the applicable event, and will have completed and / or not been discontinued from treatment. Details defining these analyses will be provided in the SAP.

New text:

For the following secondary endpoint analyses, subjects will be classified into 2 treatment groups: (1) the “standard dose” treatment group, consisting of applicable ITT subjects in Treatment Arm A, and (2) the “extended dosing” treatment group, consisting of applicable ITT subjects in Treatment Arm C. For these analyses except for rPFS, the 6th dose date will be used as the reference date. For rPFS, randomization date will be used as the reference date.

For secondary endpoint time-to-event analyses for these treatment groups, subjects included will have survived to the 6th dose date without having experienced the applicable event, and will have completed and / or not been discontinued from treatment. Details defining these analyses will be provided in the SAP.

#### **8.6 Determination of sample size**

Old text:

Comparison 2 will analyze SSE-FS from ~~24 weeks~~ in subjects surviving SSE-free to ~~24 weeks completing and / or without prior permanent discontinuation from treatment.~~(27,28) A median SSE-FS of 9 months with constant hazards is assumed for standard dose. Extended dosing is assumed to have the same SSE-FS efficacy as standard dosing for the first 24 weeks, and 65% improvement (hazard ratio 0.606) thereafter. With 240 of 360 subjects randomized to Treatment Arm A and Treatment Arm C, simulations indicated that 44.65% of randomized subjects (107.2 of 240) would have an SSE-FS event or loss to follow-up during the first 24 weeks, leaving an estimated 55.35% (132.8) surviving SSE-free and eligible for inclusion at 24 weeks. An average of 74.9 simulated events occurred for this comparison, and a 1-sided log-rank test with 0.10 significance gave approximately 80.6% power to test H02 versus HA2.

New text:

Comparison 2 will analyze SSE-FS from the 6th dose, in subjects surviving SSE-free to the 6th dose.(27,28) A median SSE-FS of 9 months with constant hazards is assumed for standard dose. Extended dosing is assumed to have the same SSE-FS efficacy as standard dosing for the first 24 weeks, and 65% improvement (hazard ratio 0.606) thereafter. With

240 of 360 subjects randomized to Treatment Arm A and Treatment Arm C, simulations indicated that 44.65% of randomized subjects (107.2 of 240) would have an SSE-FS event or loss to follow-up during the first 24 weeks, leaving an estimated 55.35% (132.8) surviving SSE-free and eligible for inclusion at 24 weeks. An average of 74.9 simulated events occurred for this comparison, and a 1-sided log-rank test with 0.10 significance gave approximately 80.6% power to test H02 versus HA2.

## Change 6

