***Section 8.6 Determination of Sample Size:***

Paragraphs 2 to 4:

Old text:

The sample .....randomized. The primary endpoint cut-off, as defined in Section 8.4, is estimated to be reached in an average of ~~55~~ months.

Comparison 1 will analyze SSE-FS..... regimen. Simulations indicated an average of ~~197.9~~ events would occur for this comparison at primary endpoint cut-off, and a 1-sided log-rank test with 0.10 significance gave approximately ~~92~~% power to test H01 versus HA1.

Comparison 2 will analyze SSE-FS .....  
.....eligible for inclusion at 24 weeks. An average of ~~80.6~~ simulated events occurred for this comparison, and a 1-sided log-rank test with 0.10 significance gave approximately ~~84~~% power to test H02 versus HA2.

New text:

The sample .....randomized. The primary endpoint cut-off, as defined in Section 8.4, is estimated to be reached in an average of 39 months.

Comparison 1 will analyze SSE-FS.....  
.regimen. Simulations indicated an average of 186.6 events would occur for this comparison at primary endpoint cut-off, and a 1-sided log-rank test with 0.10 significance gave approximately 90.5% power to test H01 versus HA1.

Comparison 2 will analyze SSE-FS .....  
.....eligible for inclusion at 24 weeks. An average of 74.9 simulated events occurred for this comparison, and a 1-sided log-rank test with 0.10 significance gave approximately 80.6% power to test H02 versus HA2.

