**Change 5:**

***Section 5.2.1 Withdrawal:***

3rd bullet:

Old text:

- A dose delay of more than 4 weeks (maximum of 8 weeks [~~± 7 days~~] between 2 injections)

New text:

- A dose delay of more than 4 weeks (maximum of 8 weeks between 2 injections)

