#### **Change 15:**

##### ***Section 5.2.1 Withdrawal Section***

5th and 6th bullets:

Old text:

- If the subject experiences any non-hematological CTCAE Grade 4 ~~toxicity~~ lasting > ~~7 days~~ despite adequate treatment
- If the subject experiences Grade 3 neutropenia or Grades 3 or 4 thrombocytopenia lasting > 2 weeks or Grade 4 neutropenia lasting > ~~7 days~~ despite adequate treatment. Blood transfusions and biologic response modifiers, such as GM-CSF or G-CSF can be used for the treatment of hematological abnormalities during the treatment period.

New text:

- If the subject experiences any non-hematological CTCAE Grade 4 adverse event lasting > 1 week despite adequate treatment regardless of causality.

- If the subject experiences Grade 3 neutropenia or Grades 3 or 4 thrombocytopenia lasting > 2 weeks or Grade 4 neutropenia lasting > 1 week despite adequate treatment regardless of causality. Blood transfusions and biologic response modifiers, such as GM-CSF or G-CSF can be used for the treatment of hematological abnormalities during the treatment period.

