### **5.2.1 Withdrawal**

Old text:

For any subject who prematurely discontinues study treatment, the EOT assessments must be completed. The subject will remain in the study throughout the follow-up period. In all cases, the reason for discontinuation from study treatment must be recorded in the electronic case report form (eCRF) and in the source documentation.

New text:

For any subject who prematurely discontinues study treatment, the EOT assessments must be completed. The subject will remain in the study throughout the follow-up period. Any subject who withdraws from the study procedures but does not withdraw consent should enter active follow-up without clinic visits for survival assessment (see Section 7.1.2.8.2). In all cases, the reason for discontinuation from study treatment must be recorded in the electronic case report form (eCRF) and in the source documentation.

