Both comparisons will be performed at the time of final analysis, after the latest of (1) approximately 135 SSE-FS events in subjects included in Comparison 1 as defined below; (2) approximately 75 SSE-FS events following the 6th dose in subjects included in Comparison 2 as defined below, and (3) the last subject has been followed for 30 days from last treatment. In the event the applicable number of events is not reached, the primary endpoint analysis will mature 7 years after the last subject has received last treatment.

Comparison 2: No further radium-223 dichloride treatment versus extended dosing: SSE-FS analysis from the date of the 6th dose in subjects receiving standard-dose regimen

H02: In a population of subjects treated with a regimen of up to 6 doses of 50 kBq/kg (55 kBq/kg after implementation of NIST update) (standard dose) radium-223 dichloride who survived SSE-free and are eligible for further radium-223 dichloride treatment at 24 weeks, population SSE-FS beyond the 6th dose in subjects treated with a regimen of up to an additional 6 doses of 50 kBq/kg (55 kBq/kg after implementation of NIST update) (extended dose) radium-223 dichloride is equal to population SSE-FS beyond the 6th dose in subjects

receiving no further radium-223 dichloride treatment beyond the standard dose regimen, versus

HA2: In a population of subjects treated with a regimen of up to 6 doses of 50 kBq/kg (55 kBq/kg after implementation of NIST update) (standard dose) radium-223 dichloride who survived SSE-free and are eligible for further radium-223 dichloride treatment at 24 weeks, population SSE-FS beyond the 6th dose in subjects treated with a regimen of up to an additional 6 doses of 50 kBq/kg (55 kBq/kg after implementation of NIST update) (extended dose) radium-223 dichloride is greater than population SSE-FS beyond the 6th dose in subjects receiving no further radium-223 dichloride treatment beyond the standard dose regimen.

Comparison 2 will be an analysis of SSE-FS from the 6th dose in subjects surviving SSE-free to the completion of the 6th dose. It will compare subjects in Treatment Arm A with subjects in Treatment Arm C.

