### **8.2 Analysis sets**

Old text:

**Week 24 (W24):** All ITT subjects in Arm A (standard dose) and Arm C (extended dosing) ~~treated with radium-223 dichloride and eligible for further treatment at W 24~~. The W24 dataset will be used for the analysis of efficacy endpoints related to Comparison 2 and associated evaluations. Subjects will be included in W24 analyses according to the treatment to which they were randomized.

New text:

**Week 24 (W24):** All ITT subjects in Arm A (standard dose) and Arm C (extended dosing) treated with radium-223 dichloride and eligible for further treatment at W 24 (i.e., 7th injection). Week 24 applies to subjects who received the 6th injection without any dose delays. As dose delays are allowed per protocol, 6th injection can occur after Week 24 for subjects who had dose delays. Hence, this population is defined based on the number of injections not based on the timing. The W24 dataset will be used for the analysis of efficacy endpoints related to Comparison 2 and associated evaluations. Subjects will be included in W24 analyses according to the treatment to which they were randomized.

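### The Comparison 2 figures in 8.6 are for entry at Week 24 with no separate allowance for stopping treatment; the current plan starts at the 6th dose in an injection-defined set, so N, timing and power need restating

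*Protocol*

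**What the plan says.** Section 8.6, in the text current since Amendment 3, assumes a 9-month median SSE-FS on standard dose with constant hazards. Extended dosing has no effect for 24 weeks and a hazard ratio of 0.606 after that. Of 240 subjects in Arms A and C, 44.65% "would have an SSE-FS event or loss to follow-up during the first 24 weeks, leaving an estimated 55.35% (132.8) surviving SSE-free and eligible" for inclusion. With 74.9 simulated events, "a 1-sided log-rank test with 0.10 significance gave approximately 80.6% power to test H02 versus HA2". The cut-off, in 8.6 as revised by Amendment 1, "is estimated to be reached in an average of 39 months".

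The population analysed is described elsewhere. The Week 24 set in 8.2 needs eligibility for the 7th injection: "Hence, this population is defined based on the number of injections not based on the timing". The Synopsis and 8.4.1 run the comparison from the 6th dose, which Table 7-1 schedules at Week 20, in subjects who reach or complete that dose. The event trigger is "approximately 75 SSE-FS events following the 6th dose in subjects included in Comparison 2".

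Section 5.2.1 lists reasons for stopping treatment. They include "A dose delay of more than 4 weeks (maximum of 8 weeks between 2 injections" (the wording continues) and "If the subject experiences any non-hematological CTCAE Grade 4 adverse event lasting > 1 week despite adequate treatment regardless of causality". Of a subject who stops treatment early it says: "The subject will remain in the study throughout the follow-up period".

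Both primary comparisons wait for the latest of the Comparison 1 event count, the Comparison 2 event count and 30 days after the last treatment. If the event counts are not reached, the fallback is 7 years after the last subject's last treatment (4.4).

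**The concern.** The sizing text and the analysis set describe different populations in two respects.

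- **Entry time.** The sizing enters subjects at Week 24. The analysis starts at the 6th dose, about four weeks earlier on schedule. The assumed effect begins only after Week 24, so the extra early events carry no treatment difference.
- **Who is removed.** The sizing removes events and losses to follow-up. The analysis set also removes subjects who stop treatment before the required injection while SSE-free and still followed. Under 5.2.1 such a subject is neither an event nor, on its face, a loss.

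Amendment 3 moved the entry point, yet 8.6 carries the same 44.65%, 132.8, 74.9 and 80.6% before and after the change. At stake are the stated power of a primary comparison and the date of both, since a shortfall in Comparison 2 events also holds back Comparison 1.

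**Working it through.** **Inputs from the protocol:** 240 subjects, taken as 1:1; 9-month median; hazard ratio 0.606 after Week 24; 1-sided alpha 0.10; 44.65% attrition; 75-event trigger; 39 months; 7-year fallback. **Not given in the part at hand:** accrual, loss rate and discontinuation rate.

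**1. Reproduce the printed power.** Schoenfeld: Φ(√74.9/2 × |ln 0.606| − 1.2816) = Φ(4.327 × 0.5009 − 1.2816) = Φ(0.886) = 81.2%. The Freedman form gives 80.0%. The printed 80.6% lies between them, and 240 × 0.5535 = 132.8. The printed figures contain no arithmetic slip.

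**2. Split the 44.65%.** λ = ln 2/9 = 0.0770 per month and 24 weeks = 5.52 months, so S = exp(−0.0770 × 5.52) = 0.654, and events remove 34.6%. The rest is 1 − 0.5535/0.654 = 15.3% loss among event-free subjects, which is 0.030 per month.

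**3. See how that loss behaves.** Continued after entry, and with uniform accrual of about 21.7 months (back-solved), it gives 74.9 Comparison 2 events at month 39. The same model gives 186.5 Comparison 1 events against 186.6 printed, if Arm B has a hazard ratio of 0.667 and Arm C is counted only to Week 24 (both inferred). One constant loss rate therefore fits both comparisons, with no separate allowance for stopping treatment.

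**4. Move entry to the 6th dose, with no discontinuation.** Week 20 = 4.60 months. N = 240 × exp(−(0.0770 + 0.0301) × 4.60) = 146.6, or 61.1%. Events between Weeks 20 and 24 = 146.6 × (0.0770/0.1072) × (1 − exp(−0.1072 × 0.92)) = 9.9. Of 75 events, about 65.1 then carry the effect. The average log hazard ratio is (65.1/75) × 0.5009 = 0.435, and power ≈ Φ(√75/2 × 0.435 − 1.2816) = Φ(0.60), about 73%. Simulation under the plan's cut-off rule gives about 72%.

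**5. Add discontinuation d among SSE-free, followed subjects** (assumed range; 6th-dose entry; loss of 0.030 per month continuing):

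| d | N = 146.6 × (1 − d) | Median cut-off, months | Chance of never reaching 75 |
|---|---|---|---|
| 0% | 146.6 | 33 | 0.1% |
| 10% | 131.9 | 37 | 3% |
| 15% | 124.6 | 42 | 12% |
| 20% | 117.3 | 51 | 30% |
| 30% | 102.6 | fallback | 80% |

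Power stays at about 72% for d from 0 to 20%. The fallback falls near month 116: 21.7 months of accrual + 10.1 months (44 weeks) to the 12th dose + 84.

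**6. Week-24 entry, for contrast.** Under the same cut-off rule, power is 80.0, 78.5, 78.9, 77.2 and 74.3% at d = 0, 10, 15, 20 and 30%; the small rise at 15% is simulation noise. The chance of never reaching 75 is 3.5, 26, 50, 73 and 97%.

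**7. Sensitivity to loss.** With no loss after entry, on the Week-24 basis, 75 events are reachable at every d up to 40%: month 38 at 20%, 46 at 30% and 68 at 40%.

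**The case against.** A reader might infer that the 75-event target and the power cannot be delivered. The documents do not support that. No discontinuation rate is given. The cut-off is driven by events, so fewer entrants first cost time, not power. Reading power off at month 39 would assume a fixed-date analysis that the plan does not contain, since 39 months is only an estimated average. Chances of missing 75 events computed from Week-24 entry (step 6) use a start point that the Synopsis and 8.4.1 no longer use.

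The 15.3% may also have been meant to cover some treatment stoppers. Subjects given further anticancer therapy move to telephone follow-up, and the Table 7-1 footnotes say SSEs are not collected by phone, so a simulation could reasonably code them as lost. Section 6.4.7 also allows treatment to continue after progression. This stands as a possibility, but 8.6 does not say it. The fit in step 3 shows that a single rate was used, not what it represents.

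Earlier entry adds subjects, which offsets about 9% discontinuation (132.8/146.6 = 0.906). That is true for numbers and timing, but the added early events are those that dilute the effect.

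Finally, 8.2 and the hypotheses still refer to eligibility at Week 24. If that were read as requiring SSE-free survival to Week 24, the dilution would disappear and step 6 would apply. The Synopsis and 8.6 ask only for SSE-free survival to the 6th dose.

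**Conclusion.** The point holds as a mismatch, not as an arithmetic error. The printed 132.8, 74.9, 39 months and 80.6% reproduce for Week-24 entry with events and losses only, and that is not the set now analysed.

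The firmest consequence does not depend on the unknown discontinuation rate: with 6th-dose entry and the effect starting after Week 24, power is about 72% against 80.6% printed. Discontinuation then mainly delays the cut-off. Failure to reach 75 events becomes a material risk at about 15 to 20% and likely at 30%, and in that case both comparisons wait for the 7-year fallback.

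These sizes rest on inferred accrual (about 21.7 months) and loss (0.030 per month). The attainability figures also need that loss to continue after entry. Timing assumes the 6th dose falls at Week 20; dose delays would move it. Only the second part of the protocol is at hand, so an allowance stated in the first part would change the discontinuation element.

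**What to change.** In 8.6:

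- State the assumed rate of permanent treatment discontinuation before the 6th/7th injection, and whether the 44.65% already includes it.
- State the entry time, and how an SSE between the 6th dose and the planned 7th injection is treated, so that 8.2, 8.4.1 and 8.6 describe one set.
- Re-run the simulation from the 6th dose for that set. The pooled observed discontinuation rate can be used and needs no efficacy unblinding.
- Restate N, expected events, cut-off month and power in place of 132.8, 74.9, 39 months and 80.6%.

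Revisit the 75-event target in 4.4 and 8.4.1 only if the re-run shows that it is unlikely to be reached; the present evidence does not justify lowering it.

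The cost is one re-run of an existing simulation and a wording change, with no extra subjects. The downside is a less favourable stated power for Comparison 2.

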### ***7.3.5.2 Time to increase in physical symptoms of disease based on FPSI-DRS-P***

Old text:

~~For each applicable baseline, time to increase in physical symptoms of disease based on (FPSI-DRS-P) will be calculated with respect to that baseline, based only on assessments through Week 48. Details, including definition of an increase, will be provided in the SAP.~~

New text:

Time to increase in physical symptoms of disease based on (FPSI-DRS-P) will be calculated with respect to baseline value collected prior to first dosing, based only on assessments through Week 48. Details, including definition of an increase, will be provided in the SAP.

